4 TREATMENT(S)

4.1 Identification of Investigational Product(s)

4.1.1 Test Drug(s)

Mirabegron will be supplied as 25 mg and 50 mg OCAS (Oral Controlled Absorption System) modified release tablets. Mirabegron OCAS tablets contain the following excipient: Polyethylene Oxide 2000000 NF, Polyethylene Glycol 8000 NF, Hydroxypropyl Cellulose NF, Butylated Hydroxytoluene NF, and Magnesium Stearate NF. The tablets are film coated

using Opadry® 03F43159 (25 mg) and 03F42192 (50 mg). The opadry formulation contains: Hypromellose USP, Polyethylene Glycol 8000, Yellow Ferric Oxide NF and Red Ferric Oxide NF.

The mirabegron tablets are packaged in blisters and must be stored at room temperature, 25°C (77°F); excursion permitted to 15°-30°C (59°-86°F).

The clinical trial material of mirabegron OCAS tablets have been manufactured for Astellas by Astellas Pharma Technologies, Inc.

All investigational materials must be kept in a secure area inaccessible to unauthorized individuals.

4.1.2 Concomitant Medication

Tamsulosin hydrochloride will be supplied as 0.4 mg capsules (US) / tablets (EU/CA) in either commercial blister packs or commercial bottles. All storage and handling information can be found in the product package insert or the Summary of Product Characteristics (SPC).

4.1.3 Placebo

The placebo to match (PTM) mirabegron OCAS tablets contain Polyethylene Oxide 2000000 NF, Polyethylene Glycol 8000 NF, Hydroxypropyl Cellulose NF, Butylated Hydroxytoluene NF, and Magnesium Stearate NF. The tablets are film coated using Opadry® 03F42192 which contains: Hypromellose USP, Polyethylene Glycol 8000, Yellow Ferric Oxide and Red Ferric Oxide NF.

The PTM mirabegron OCAS tablets have been manufactured for Astellas by Astellas Pharma Technologies, Inc.

The mirabegron PTM tablets are packaged in blisters. The blisters must be stored at room temperature, 25°C (77°F); excursions permitted to 15°-30°C (59°-86°F).

4.2 Packaging and Labeling

All medication used in this study will be prepared, packaged, and labeled in accordance with AUST Standard Operating Procedures (SOPs), Good Manufacturing Practice (GMP) guidelines, ICH GCP guidelines, and applicable local laws/regulations.

All Investigational Medicinal Products will bear a label conforming to regulatory guidelines, Good Manufacturing Practice and local laws and regulations which identifies the contents as investigational drug.

4.3 Study Drug Handling

Current ICH GCP Guidelines require the Investigator to ensure that study drug deliveries from the Sponsor are received by the Investigator/or designee and

- that such deliveries are recorded,
- that study drug is handled and stored according to labeled storage conditions,
- that study drug is only dispensed to study subjects in accordance with the protocol, and

- that any unused study drug is returned to the Sponsor or standard procedures for the alternative disposition of unused study drug are followed.

The supplied study drug should **not** be stored at a temperature outside the temperature range specified on the study drug label. Any temperature excursion outside the temperature range should be evaluated by the Sponsor.

Drug inventory and accountability records for the study drugs will be kept by the Investigator/or designee. Study drug accountability throughout the study must be documented and reconciled. The following guidelines are therefore pertinent:

- The Investigator agrees not to supply study drugs to any persons except the eligible subjects in this study in accordance with the protocol.
- The Investigator or designee will keep the study drugs in a pharmacy or other locked and secure storage facility under controlled storage conditions, accessible only to those authorized by the Investigator to dispense these test drugs.
- A study drug inventory will be maintained by the Investigator or designee. The inventory will include details of material received and a clear record of when they were dispensed and to which subject.
- At the conclusion or termination of this study, the Investigator or designee agrees to conduct a final drug supply inventory and to record the results of this inventory on the Drug Accountability Record. It must be possible to reconcile delivery records with those of used and/or returned medication. Any discrepancies must be accounted for and documented. Appropriate forms of deliveries and returns must be signed by the site staff delegated this responsibility.
- The site must return study drug to the Sponsor or designee at the end of the study or upon expiration.

4.4 Blinding

4.4.1 Blinding Method

This is a randomized, double-blind, placebo-controlled, parallel group study. Randomization will be stratified by geographic region (NA, EU). Subjects will be assigned to a treatment group in the order which they meet the criteria for randomization. After the completion of the 4-week open label tamsulosin hydrochloride run-in period, subjects will be randomized to either 25 mg mirabegron or PTM for 4 weeks of treatment and then an obligatory increase to mirabegron 50 mg or 50 mg PTM for the remainder of the study. Subjects will receive their allocated treatment according to a computer-generated randomization schedule prepared by the Sponsor or designee prior to the start of the study. The subject, Investigator and Sponsor will not be aware of the treatment regimen.

4.4.2 Confirmation of the Indistinguishability of the Study Drugs

Mirabegron and mirabegron PTM tablets will be used in this study. The mirabegron PTM will be identical in size, color and appearance to the mirabegron 25 mg and mirabegron 50 mg tablets.

4.4.3 Retention of the Assignment Schedule and Procedures for Treatment Code Breaking

Study drug treatment may be revealed only for reasons relating to the subject's safety and when critical therapeutic decisions are contingent on knowing the assigned study drug.

Withdrawal of a subject from the study (refer to Section 6.1) is not a sufficient reason to break the study blind. Any decision to break the blind should be discussed with the Astellas Study Physician (refer to Section II for contact information).

If the blind is broken for a subject, the reason is to be documented as a written entry in the source document. Key information will be recorded at the time when the blind is broken. This includes the date the blind was broken, the reason, the person who requested the breaking of the blind, the name of the person who broke the blind, and the name of the Astellas representative contacted.

4.4.4 Breaking the Treatment Code for Emergency

In order to break the treatment code (unblinding) for a subject, the assigned study medication information is accessible through the IWRS. The Sponsor must be notified immediately if the blind is broken. The date, time, and reason the blind was broken must be recorded in the source documents and on the appropriate Electronic Case Report Form (eCRF) if applicable.

Breaking the treatment code, or unblinding of an individual subject's treatment assignment, may be done only for reasons relating to subject safety or when critical therapeutic decisions are contingent upon knowing the blinded study drug assignment.

4.4.5 Breaking the Treatment Code by the Sponsor

The Sponsor may break the treatment code for subjects who experience a Suspected Unexpected Serious Adverse Reaction (SUSAR), in order to determine if the individual case or a group of cases requires expedited regulatory reporting. Individual Emergency Codes will be provided to the limited staff, who are responsible to break the codes for all SUSAR cases for reporting purposes.

4.5 Assignment and Allocation

After a subject signs informed consent, a subject number will be assigned. To obtain a subject number, the Investigator or designee will utilize a web or phone-based Interactive Response Technology (IRT), available seven days a week and 24 hours a day.

Subjects who meet all the inclusion and none of the exclusion criteria will enter a 4-week tamsulosin hydrochloride 0.4 mg capsule (US) / tablet (EU/CA) run-in period (Visit 1). At Visit 2 (Baseline), subjects will be randomly assigned to receive mirabegron or placebo using a 1:1 randomization schedule. Randomization will be stratified by geographic region (NA, EU).

To obtain the randomization treatment, the Investigator or designee will utilize a web or phone-based IRT, available seven days a week and 24 hours a day. After submitting certain information about the eligible subject, the randomized drug assignment will be provided by

the IRT. Study drug assignment will remain blinded to all staff. Each study drug will be preprinted with a Medication ID number. The Medication ID number assigned to the subject will be noted in the electronic case report form (eCRF) for study drug.

Once a subject number is assigned, if the corresponding subject does not receive study drug, the subject number will not be used again.

5 TREATMENTS AND EVALUATION

5.1 Dosing and Administration of Study Drug(s) and Other Medication(s)

5.1.1 Dose/Dose Regimen and Administration Period

Subjects will be randomized to one of two treatment groups in a 1:1 ratio to either mirabegron or placebo (PTM). Those subjects randomized to mirabegron will start at 25 mg tablet QD for 4 weeks along with tamsulosin hydrochloride 0.4 mg capsule (US) / tablet (EU/CA). Mirabegron dose will be titrated to mirabegron 50 mg QD at 4 weeks. Mirabegron 50 mg dose will be maintained for the remaining 8 weeks of the study along with tamsulosin hydrochloride capsule 0.4 mg (US) / tablet (EU/CA). Oral mirabegron can be taken with or without food, but during the course of the study will be taken the same time each day as the concomitant tamsulosin hydrochloride medication.

Those subjects randomized to placebo will start placebo to match (PTM) mirabegron 25 mg tablet QD for 4 weeks along with tamsulosin hydrochloride 0.4 mg capsule (US) / tablet (EU/CA). PTM mirabegron 25 mg will be increased to PTM mirabegron 50 mg and will be maintained for the remaining 8 weeks of the study along with tamsulosin hydrochloride 0.4 mg capsule (US) / tablet (EU/CA). Subjects will be instructed to take PTM at the same time each day as the concomitant tamsulosin hydrochloride medication.

Subjects will be instructed to take oral tamsulosin hydrochloride 0.4 mg approximately one-half hour following the same meal each day.

5.1.2 Increase or Reduction in Dose of the Study Drug(s)

The study design employs a dose increase from 25 mg mirabegron to 50 mg mirabegron at Week 4 (Visit 3). Once a patient has increased dose, he will remain on that dose for the remainder of the study unless for safety reasons that require discontinuation of study drug.

5.1.3 Previous and Concomitant Treatment (Medication and Non-Medication Therapy)

5.1.3.1 Previous Medication (Drugs and Therapies)

The Investigator must record the use of previous (all medication taken within 30 days prior to Screening [Visit 1]) and current concomitant treatment, both drug and non-drug therapies, prescribed and over-the-counter and all alternative medicines, in the eCRFs. This also includes drugs used on a chronic and as-needed basis.

Subjects must be instructed not to start any new medication, both prescribed and over-the-counter, without consulting the Investigator, unless the new medication is required for emergency use. Subjects must be instructed to notify the Investigator immediately if medications were required for emergency use.

5.1.3.2 Concomitant Medication (Drugs and Therapies)

Concomitant medications will be captured from Screening/tamsulosin hydrochloride run-in (Visit 1) through the Follow-Up Phone Call (Visit 6).

Prohibited Medications (Appendix 1, part A)

Medications prohibited between Screening/tamsulosin hydrochloride run-in (Visit 1) and Week 16/Follow-up phone call (Visit 6) include other alpha-adrenergic blockers, anticholinergics, antispasmodics, strong and moderate inhibitors of CYP2D6 with narrow therapeutic index, specifically thioridazine, flecainide, propafenone, amitriptyline, paroxetine, and terbinafine, and moderate and strong inhibitors of CYP3A4 (see [Appendix 1](#) Part A). These medications must have been discontinued at least 30 days prior to Screening/tamsulosin hydrochloride run-in (Visit 1). Current or previous use of mirabegron within 6 months prior to Screening (Visit 1) is also prohibited.

Restricted Medications (Appendix 1, part B)

Medications restricted between Screening/tamsulosin hydrochloride run-in (Visit 1) and Week 16/Follow-up Phone Call (Visit 6) include loop diuretics, 5-Alpha reductase inhibitors and PDE5 inhibitors (see [Appendix 1](#) Part B). These medications are permitted provided the subject has been taking the medication on a long-term basis, i.e. has not stopped, or started, or changed dose within the 30 days prior to Screening/tamsulosin hydrochloride run-in (Visit 1), no new drug of the same class has been added to the regimen within the 30 days prior to Screening/tamsulosin hydrochloride run-in (Visit 1), and the subject remains on the medication at the same dose during the course of the study. For 5-alpha reductase inhibitors the subject must have been taking the medication for at least 6 months. No alpha-blockers other than tamsulosin hydrochloride are allowed. Intermittent use of PDE5 inhibitors (e.g. tadalafil) for treating erectile dysfunction (ED) is allowed. PDE5 inhibitors that are taken on a daily basis for the management of LUTS are not allowed.

Restricted Non-Drug Therapy

Subjects participating in any behavioral modification therapy (i.e., pelvic floor exercises, Kegel exercises, biofeedback, timed voiding, etc.) or other nondrug therapy must have started the therapy within 30 days prior to Screening/tamsulosin hydrochloride run-in (Visit 1) and must continue the same schedule through Follow-Up Phone Call (Visit 6). Neurostimulation for OAB is a strict exclusion criterion.

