3.3 Exclusion Criteria

Exclusion Criteria assessed at Visit 1 (Screening).

Subject will be excluded from participation if any of the following apply:

1. Subject has PVR > 200 mL.
2. Subject has $Q_{\max} < 5.0$ mL/second with a minimum voided volume of 125 mL.
3. Subject has hematuria > 3 rbc/hpf that has not been fully evaluated.
4. Subject has evidence of Urinary Tract Infection (UTI). Urine culture and sensitivity will be performed for positive leukocytes, nitrites, or turbidity, or at the Investigator's discretion, and will be confirmed with a culture greater than 100,000 cfu/mL. If a subject has a UTI, at Screening (Visit 1) the subject may be rescreened after successful treatment of the UTI (confirmed by a laboratory result of negative urine culture).
5. Subject has neurogenic bladder (spinal cord injury, multiple sclerosis, Parkinson's etc.).
6. Subject has diabetic neuropathy.

7. Previous open, robotic or minimally invasive prostate surgery (including transurethral procedures). Planned (scheduled) pelvic or prostate surgery planned during the study period.
8. Planned (scheduled) cataract or glaucoma surgery during the study period.
9. Subject with significant stress incontinence as determined by the Investigator.
10. Subject with clinically significant bladder outlet obstruction as determined by the Investigator.
11. Subject has an indwelling catheter or practices intermittent self-catheterization.
12. Subject has experienced 3 or more episodes of recurrent urinary tract infection within the last 12 months.
13. Subject has a symptomatic urinary tract infection, prostatitis, chronic inflammation such as interstitial cystitis, bladder stones, previous pelvic radiation therapy, or previous or current malignant disease of the pelvic organs (i.e., within the confines of the pelvis including the bladder, prostate and rectum; organs of the lower gastrointestinal tract are not necessarily considered pelvic organs as the distal ascending colon, the full transverse colon and proximal portion of the descending colon are in the abdomen).
14. Subject has received intravesical injection in the past 12 months with botulinum toxin, resiniferatoxin, or capsaicin.
15. Subject has ever received electro-stimulation therapy for OAB (e.g., sacral nerve stimulation or Percutaneous Tibial Nerve Stimulation [PTNS]).
16. Subject began or has changed a bladder training program or pelvic floor exercises less than 30 days prior to Screening.

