17. Subject has postural hypotension or syncope or postural orthostatic tachycardia.
18. Subject has moderate or severe hepatic impairment defined as Child-Pugh Class B or C.
19. Subject has severe renal impairment defined as estimated creatinine clearance less than 29 mL/min/1.73 m² as determined by central laboratory calculation of eGFR. A subject with End Stage Renal Disease (ESRD) or undergoing dialysis is also not a candidate for the study.
20. Subject has severe uncontrolled hypertension, which is defined as a sitting systolic blood pressure ≥ 180 mmHg and/or diastolic blood pressure ≥ 110 mmHg.
21. Subject has baseline resting pulse rate < 60 BPM or > 90 BPM.
22. Subject has evidence of QT prolongation on Screening (Visit 1) or Baseline (Visit 2) electrocardiogram (ECG) defined as QTcF > 450 msec.
23. Subject has a clinically significant ECG abnormality, as determined by the Investigator.
24. Subject has AST or ALT $> 2x$ upper limit of normal (ULN), or γ -GT $> 3x$ ULN and considered clinically significant by the Investigator.

25. Subject has a hypersensitivity to any components of mirabegron, tamsulosin hydrochloride, or any of the inactive ingredients.
26. Subject has a history of angioedema.
27. Subject has any clinically significant condition, which in the opinion of the Investigator makes the subject unsuitable for study participation.
28. Subject has been treated with an experimental device within 28 days or received an investigational agent within 28 days or 5 half-lives, whichever is longer, prior to Screening.
29. Subject has a concurrent malignancy or history of any malignancy (within the past 5 years), except non-metastatic basal or squamous cell carcinoma of the skin that has been treated successfully.
30. Subject has ongoing alcohol and/or drug abuse.
31. Subject is using prohibited medications defined in [Appendix 1](#) Part A within 30 days prior to Screening (Visit 1) through Follow-Up Phone Call (Visit 6).
32. Subject has stopped, started or changed the dose of a restricted medication (defined in [Appendix 1](#) Part B) within the 30 days prior to Screening (Visit 1) through Follow-Up Phone Call (Visit 6).
33. Subject has participated in an interventional trial within 30 days prior to Screening (Visit 1).
34. Subject is involved in the conduct of the study as an employee of the Astellas group, third party associated with the study, or the study site team.

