7.8 Protocol Deviations and Other Analyses

Protocol deviations as defined in Section 8.1.6 Protocol Deviations will be summarized for all randomized subjects by treatment group and total as well as by site. A data listing will be provided by site and subject.

The protocol deviation criteria will be uniquely identified in the summary table and listing. The unique identifiers will be as follows:

PD1 - Entered into the study even though they did not satisfy entry criteria,

PD2 - Developed withdrawal criteria during the study and was not withdrawn,

PD3 - Received wrong treatment or incorrect dose,

PD4 - Received excluded concomitant treatment.

Any other analyses will be specified in the Statistical Analysis Plan (SAP).

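### The non-drug therapy rule in Protocol 5.1.3.2 and the synopsis is worded backwards: it requires a recent start, against exclusion 16 for pelvic floor exercises and bladder training

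*Protocol*

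**What the plan says.** Three rules in the protocol use a 30-day window before Screening and bear on this point.

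- **Non-drug therapy** (5.1.3.2, Restricted Non-Drug Therapy; same wording in the synopsis). A man in any behavioural modification therapy, with pelvic floor and Kegel exercises, biofeedback and timed voiding given as examples, or in other non-drug therapy, "must have started the therapy within 30 days prior to Screening/tamsulosin hydrochloride run-in (Visit 1) and must continue the same schedule" up to Visit 6.
- **Exclusion 16** (3.3, repeated in the synopsis). Not eligible: "Subject began or has changed a bladder training program or pelvic floor exercises less than 30 days prior to Screening".
- **Restricted medications** (5.1.3.2). Permitted only if the man "has not stopped, or started, or changed dose within the 30 days prior to Screening/tamsulosin hydrochloride run-in (Visit 1"). Exclusion 32 mirrors this; it begins "Subject has stopped, started or changed the dose of a restricted medication" and applies the same 30-day window.

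For prohibited medications, section 5.1.3.2 uses a different expression: "These medications must have been discontinued at least 30 days prior to Screening/tamsulosin hydrochloride run-in (Visit 1").

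Section 4.5 lets a man into the run-in if he meets every inclusion criterion and no exclusion criterion. Waivers are not allowed (3.3 and 8.1.6).

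**The concern.** Rules of this kind normally keep background therapy stable, so that a recently begun exercise programme is not still taking effect while the drug is being assessed. Exclusion 16 and the restricted-medication rule both do that. The non-drug paragraph does the opposite: taken at its word, it admits the man who took up exercises last week and rules out the man who has done them for years.

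What is at stake is consistent handling. For pelvic floor exercises a site has two instructions pointing in opposite directions, and nothing in the protocol says which prevails. One site may decline a stable user because of 5.1.3.2, while another enrols him because he passes exclusion 16. For therapies that exclusion 16 does not name, the literal rule stands alone and selects men whose background treatment is newest. The primary endpoint is micturition frequency, which such therapy may influence.

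**Working it through.** The plan gives no figure on this point, and the sample size does not enter. The check is a comparison of rules. Let *d* be the number of whole days from the start of therapy to Screening.

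**Step 1. Therapies named in exclusion 16.** Pelvic floor exercises appear in both rules, so no interpretation is needed. Bladder training is not listed by name in 5.1.3.2; I take it to fall under behavioural modification, with timed voiding as its nearest listed form.

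| Rule | Admits |
|---|---|
| 5.1.3.2 and synopsis | *d* ≤ 30 |
| Exclusion 16 | *d* ≥ 30 (bars *d* < 30) |
| Both | *d* = 30 only |

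Section 5.1.3.2 admits 31 start days (*d* = 0 to 30). Exclusion 16 bars 30 of them (*d* = 0 to 29), and 31 − 30 = 1 remains. If the 5.1.3.2 window is read strictly as *d* < 30, none remains.

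**Step 2. Men outside the overlap.**
- *d* = 0 to 29: meets 5.1.3.2, barred by exclusion 16.
- *d* > 30: passes exclusion 16, breaches 5.1.3.2. This is the stable user whom exclusion 16 evidently means to let in.

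**Step 3. Therapies not named in exclusion 16** (biofeedback, other non-drug therapy). Only *d* ≤ 30 applies. There is no contradiction, but only recent starters are admitted. For a restricted drug, the same section admits only men with no start, stop or dose change in those 30 days.

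**Step 4. Can the wording be read the other way?** The prohibited-medication paragraph says *at least* 30 days where it means that. The restricted-medication paragraph and exclusion 32 use *within* for the window in which a start is not allowed. Reading *within* as *at least* in the non-drug paragraph alone would give the word opposite senses in neighbouring paragraphs. The body and the synopsis carry the same wording, so neither corrects the other, and no other section does.

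**The case against.** The strongest reply is that entry does not turn on this sentence. Section 4.5 ties entry to the numbered inclusion and exclusion criteria, and 5.1.3.2 is not among them. Exclusions 31 and 32 bring in Appendix 1 Parts A and B, which list drugs only. Exclusion 16 already points the sensible way, and a careful site would follow it. This stands, and it is why the point is minor. It does not remove the inconsistency, because the sentence is a mandatory instruction.

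Four stronger readings are tempting, and the documents do not support them.

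- **That no site can follow both rules.** A start at exactly 30 days satisfies both, men not on such therapy are untouched, and a site that declines all other users breaks neither rule. The accurate statement is that almost no user of these therapies satisfies both.
- **That the whole non-drug rule contradicts exclusion 16.** The exclusion names only bladder training and pelvic floor exercises. For the rest, the contrast with the medication rule shows likely drafting intent and is not a second contradiction.
- **That deviation tables will be distorted.** Section 5.1.3.1 has sites record "current concomitant treatment, both drug and non-drug therapies", so a site might log a stable user under "PD1 - Entered into the study even though they did not satisfy entry criteria" or under "PD4 - Received excluded concomitant treatment". Neither fits well: he meets the numbered criteria on this point, and the therapy is headed restricted, not prohibited. Misclassification is possible but conjectural.
- **That the primary comparison is biased or loses power.** Nothing shows this. Randomization should balance such therapy between arms, and any added noise cannot be sized from the protocol.

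A last objection concerns timing. This version is dated 22 January 2018, the planned period ends in 2Q2018, and participation lasts about 20 weeks. If that plan held, counting 140 days back from 30 June 2018 puts the last Screening at about 10 February 2018. An amendment would then guide little enrolment, so the note to sites is the more useful part of the remedy.

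**Conclusion.** The point holds as a minor wording error in an operative rule, present in section 5.1.3.2 and in the synopsis. For pelvic floor exercises it contradicts exclusion 16 outright. For bladder training it does so provided that counts as behavioural modification therapy. Of the 31 start days that 5.1.3.2 allows, exclusion 16 leaves one, or none on the stricter reading, and every user established for more than 30 days is in breach of 5.1.3.2. For biofeedback and other non-drug therapy the rule is uncontradicted but reverses the stability principle applied to restricted drugs.

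That the sponsor meant *at least* 30 days is an inference from exclusion 16 and the medication rules; the protocol does not say so. The number of men affected is unknown, because the protocol gives no share on non-drug therapy. The consequence is limited to uneven handling of these men across sites.

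**What to change.** In section 5.1.3.2 and in the synopsis, replace the start requirement with one that the therapy began at least 30 days before Screening and has not changed since. Keep the requirement to hold the same schedule through Visit 6, and leave exclusion 16 as it is. Send sites a short clarification that stable users who pass exclusion 16 are eligible and are not to be recorded as deviations. Men already enrolled who met the numbered criteria in force should not be reclassified.

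The cost is one phrase in two places and one note to sites. The text change follows the amendment procedure in section 8.3.3, with IRB/IEC approval if the sponsor classes it as substantial. No new data are needed, and sample size and analysis do not change.
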